#### **7.1.1 Administrative Procedures**

##### **7.1.1.1 Informed Consent**

The Investigator must obtain documented consent from each potential subject prior to participating in a clinical trial.

###### **7.1.1.1.1 General Informed Consent**

Consent must be documented by the subject's dated signature or by the subject's legally acceptable representative's dated signature on a consent form along with the dated signature of the person conducting the consent discussion.

A copy of the signed and dated consent form should be given to the subject before participation in the trial.

The initial informed consent form, any subsequent revised written informed consent form and any written information provided to the subject must receive the IRB/ERC's approval/favorable opinion in advance of use. The subject or his/her legally acceptable representative should be informed in a timely manner if new information becomes available that may be relevant to the subject's willingness to continue participation in the trial. The communication of this information will be provided and documented via a revised consent form or addendum to the original consent form that captures the subject's dated signature or by the subject's legally acceptable representative's dated signature.

Specifics about a trial and the trial population will be added to the consent form template at the protocol level.

The informed consent will adhere to IRB/ERC requirements, applicable laws and regulations and Sponsor requirements.

### **7.1.1.2 Inclusion/Exclusion Criteria**

All inclusion and exclusion criteria will be reviewed by the investigator or qualified designee to ensure that the subject qualifies for the trial.

### **7.1.1.3 Medical History**

A medical history will be obtained by the investigator or qualified designee. Medical history will include all active conditions, and any condition diagnosed within the prior 10 years that are considered to be clinically significant by the Investigator. Details regarding the disease for which the subject has enrolled in this study will be recorded separately and not listed as medical history.

### **7.1.1.4 Prior and Concomitant Medications Review**

#### **7.1.1.4.1 Prior Medications**

The investigator or qualified designee will review prior medication use, including any protocol-specified washout requirement, and record prior medication taken by the subject within 28 days before starting the trial. Treatment for the disease for which the subject has enrolled in this study will be recorded separately and not listed as a prior medication.

#### **7.1.1.4.2 Concomitant Medications**

The investigator or qualified designee will record medication, if any, taken by the subject during the trial. All medications related to reportable SAEs and ECIs should be recorded as defined in Section 7.2.

### **7.1.1.5 Disease Details and Treatments**

#### **7.1.1.5.1 Disease Details**

The investigator or qualified designee will obtain prior and current details regarding disease status.

#### **7.1.1.5.2 Prior Treatment Details**

The investigator or qualified designee will review all prior cancer treatments including systemic treatments, radiation and surgeries.

#### **7.1.1.5.3 Subsequent Anti-Cancer Therapy Status**

The investigator or qualified designee will review all new anti-neoplastic therapy initiated after the last dose of trial treatment. If a subject initiates a new anti-cancer therapy within 30 days after the last dose of trial treatment, the 30day Safety Follow-up visit must occur before the first dose of the new therapy. Once new anti-cancer therapy has been initiated the subject will move into survival follow-up.

### **7.1.1.6 Assignment of Screening Number**

All patients will be assigned a study identification number (sequential number based on when first screened for participation in the trial, which will become the study ID once the patient is registered and starts treatment) and a random database number.

### **7.1.1.7 Trial Compliance (Medication/Diet/Activity/Other)**

Drugs will be administered intravenously in the infusion rooms; doses and date and timing will be abstracted from the Pharmacy records and nursing notes

## **7.1.2 Clinical Procedures/Assessments**

### **7.1.2.1 Adverse Event (AE) Monitoring**

The investigator or qualified designee will assess each subject to evaluate for potential new or worsening AEs as specified in the Trial Flow Chart and more frequently if clinically indicated. Adverse experiences will be graded and recorded throughout the study and during the follow-up period according to NCI CTCAE Version 4.0 (see Section 11.2). Toxicities will be characterized in terms regarding seriousness, causality, toxicity grading, and action taken with regard to trial treatment.

For subjects receiving treatment with pembrolizumab all AEs of unknown etiology associated with pembrolizumab exposure should be evaluated to determine if it is possibly an event of clinical interest (ECI) of a potentially immunologic etiology (termed immune-related adverse events, or irAEs); see the separate ECI guidance document in Appendix 4 regarding the identification, evaluation and management of potential irAEs.

Please refer to section 7.2 for detailed information regarding the assessment and recording of AEs.

### **7.1.2.2 Full Physical Exam**

The investigator or qualified designee will perform a complete physical exam during the screening period. Clinically significant abnormal findings should be recorded as medical history. A full physical exam should be performed during screening,

### **7.1.2.3 Directed Physical Exam**

For cycles that do not require a full physical exam per the Trial Flow Chart, the investigator or qualified designee will perform a directed physical exam as clinically indicated prior to trial treatment administration.

### **7.1.2.4 Vital Signs**

The investigator or qualified designee will take vital signs at screening, prior to the administration of each dose of trial treatment and at treatment discontinuation as specified in

the Trial Flow Chart (Section 6.0). Vital signs should include temperature, pulse, respiratory rate, weight and blood pressure. Height will be measured at screening only.

#### **7.1.2.5 Eastern Cooperative Oncology Group (ECOG) Performance Scale**

The investigator or qualified designee will assess ECOG status (see Section 11.1) at screening, prior to the administration of each dose of trial treatment and discontinuation of trial treatment as specified in the Trial Flow Chart.

#### **7.1.2.6 Tumor Imaging and Assessment of Disease**

Contrast computed tomography covering the chest, abdomen and pelvis per study calendar every 2 cycles is the modality of choice for assessment of response using RECIST 1.1 criteria. For patients in the head and neck cancer cohort, a neck soft tissue CT scan will be included. Patients in the non-small cell lung cohort will have soft tissue neck imaging included only if there was known measurable disease in that location at baseline. Patients who have no disease in the pelvis at baseline, and no pelvic symptoms may have the pelvic portion of the CT omitted.

#### **7.1.2.7 Tumor Tissue Collection and Correlative Studies Blood Sampling**

Tumor biopsy collection methodology will be determined by the investigator and should occur from the safest anatomic site. If there is no site deemed safe for biopsy by the treating investigator the biopsy procedure will be omitted.

Exploratory blood biomarker specimens are collected at enrollment, and every 4 cycles. 2 blood collection tubes (EDTA and Streck Cell Free RNA BCT) will be sent at room temperature to:

**USC/Norris Cancer Center, [name] Laboratory**  
**[name]**  
**[name]**  
**[contact]**

Blood specimens for anti-drug antibodies and serum banking (serum separator tube) will be collected at baseline, cycle 1,2, 8 and every 8th cycle thereafter. These will also be sent to the [name] Laboratory for long term storage.

An additional blood collection tube (Streck Cell Free DNA BCT) will be sent at baseline and every 4 cycles as a CTC specimen to the [name] Laboratory.

#### **Handling of CTC specimens**

Packages must be shipped the same day of sample collection to ensure processing within 24 hours of collection time. Please select:

- 1. Priority Overnight**
- 2. No signature required**

**3. Email Notifications** going to [[contact]](mailto:[contact]) as recipient. Select all notifications types: ship, tendered, exception, and delivery.

Samples collected on Monday to Thursday must be shipped to:

### **7.1.3 Laboratory Procedures/Assessments**

Details regarding specific laboratory procedures/assessments to be performed in this trial are provided below. Laboratory Safety Evaluations (Hematology, Chemistry and Urinalysis)

Laboratory tests for hematology, chemistry, urinalysis, and others are specified in Table 5.

Table 5 Laboratory Tests

Hematology	Chemistry	Urinalysis	Other
Hematocrit	Albumin	Blood	Serum $\beta$ -human chorionic gonadotropin†
Hemoglobin	Alkaline phosphatase	Glucose	( $\beta$ -hCG)†
Platelet count	Alanine aminotransferase (ALT)	Protein	PT (INR)
WBC (total and differential)	Aspartate aminotransferase (AST)	Specific gravity	aPTT
Red Blood Cell Count	Lactate dehydrogenase (LDH)	Microscopic exam ( If abnormal )	Total triiodothyronine (T3)
Absolute Neutrophil Count	Carbon Dioxide ‡	results are noted	Free thyroxine (T4)
Absolute Lymphocyte Count	( $CO_2$ or bicarbonate)	Urine pregnancy test †	Thyroid stimulating hormone (TSH)
	Uric Acid		PK
	Calcium		
	Chloride		Blood for correlative biomarker studies
	Glucose		Stored serum for anti-drug antibodies
	Phosphorus		
	Potassium		
	Sodium		
	Magnesium		
	Total Bilirubin		
	Direct Bilirubin ( If total bilirubin is elevated above the upper limit of normal )		
	Total protein		
	Blood Urea Nitrogen		

† Perform on women of childbearing potential only. If urine pregnancy results cannot be confirmed as negative, a serum pregnancy test will be required.

‡ If considered standard of care in your region.

Laboratory tests for screening or entry into the Second Course Phase should be performed within 10 days prior to the first dose of treatment. After Cycle 1, pre-dose laboratory procedures can be conducted up to 72 hours prior to dosing. Results must be reviewed by the investigator or qualified designee and found to be acceptable prior to each dose of trial treatment.

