## 5.2 Trial Treatments

The treatment to be used in this trial is outlined below in Table 2

Table 2 Trial Treatment

Drug	Dose/Potency	Dose Frequency	Route of Administration	Regimen/Treatment Period	Use
Pembrolizumab	200 mg IV	Q3W	IV infusion	Day 1 of each 3 week cycle	Experimental
sEphB4-HSA	10 mg/kg	Q1W	IV infusion	Day 1, 8,15 of each 3 week cycle	Experimental

Trial treatment should begin on the day of randomization or as close as possible to the date on which treatment is allocated/assigned. Trial therapy will continue up to 24 months, until disease progression, unacceptable toxicity, withdrawal of consent, investigator discretion, or sponsor decision to terminate the trial. Patients who stop therapy after 24 months and experience subsequent disease progression, may resume therapy for another 24 months.

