#### Dose Modification Guidelines for sEphB4-HSA-Related Adverse Event

Toxicity	Hold Treatment For Grade	Timing for Restarting Treatment	Discontinue Subject
Unmanageable  non-hematologic toxicity other than alopecia	3-4	
Toxicity resolves to Grade 0-1 or baseline, one dose level reduction.
 
Patients with toxicities that are manageable with supportive therapy may not require dose reductions (for example, patients with Grade 3-4 nausea, vomiting or diarrhea must have persistent toxicity despite having received optimal supportive therapy in order to require a dose reduction). Patients with <math>\geq</math> Grade 3 electrolyte abnormalities, if easily managed medically (return to Grade 2 or less within 72 hours), do not require a dose reduction.
	Treatment can be continued with supportive management as described in 5.6.1
AST, ALT	2	
Subjects who experience a grade 2 AST and or ALT will have subsequent doing held until the AST/ALT return to grade 0/1 and then can resume the prior dose, however, if the return to grade 0/1 takes longer than 7 days, the subject will be treated at a 1 level dose reduction
 
Grade 3 AST and/or ALT that represents at least a two grade increase from baseline or <math>\text{AST/ALT} \geq 10 \times \text{ULN}</math> –hold therapy, recheck weekly, initiate retreatment when resolved to baseline with one dose level reduction.
	Toxicity does not resolve within 12 weeks of last dose.
	3-4	Permanently discontinue (see exception below) 	Permanently discontinue
Hypertension 	2	Initiate antihypertensive drugs	Treatment can continue while antihypertensive drugs are initiated

Toxicity	Hold Treatment For Grade	Timing for Restarting Treatment	Discontinue Subject
	3	First occurrence, if asymptomatic and on antihypertensive therapy, may continue treatment, and optimize antihypertensive therapy.  Second occurrence, despite antihypertensive therapy, hold until grade < 3, one dose level reduction	Treatment can continue while antihypertensive drugs are initiated
	4	Permanently discontinue sEphB4-HSA	Permanently discontinue sEphB4-HSA
Thrombocytopenia	3-4	Toxicity resolves to Grade 0-1, one dose level reduction	Toxicity does not resolve within 12 weeks of last dose.
Neutropenia	4	Toxicity resolves to Grade 0-1, one dose level reduction	Treatment can continue with GCSF support

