### 5.2.2 Timing of Dose Administration

Trial treatment should be administered on Day 1 of each cycle after all procedures/assessments have been completed as detailed on the Trial Flow Chart (Section 6.0). Trial treatment may be administered up to 3 days before or after the scheduled Day 1 of each cycle due to administrative reasons.

All trial treatments will be administered on an outpatient basis.

Pembrolizumab 200 mg will be administered as a 30 minute IV infusion every 3 weeks. Sites should make every effort to target infusion timing to be as close to 30 minutes as possible. However, given the variability of infusion pumps from site to site, a window of -5 minutes and +10 minutes is permitted (i.e., infusion time is 30 minutes: -5 min/+10 min).

sEphB4-HSA will be administered as a 60 minute +/- 10 min infusion every week. The infusion will be initiated after completion of the pembrolizumab infusion.

The Each Pharmacy Manual contains specific instructions for the preparation of the pembrolizumab sEphB4-HSA and infusion fluid and administration of infusion solution.

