## 6.0 TRIAL FLOW CHART

### 6.1 Study Flow Chart

Trial Period:	Screening Phase		Treatment Cycles a								End of Treatment	Post-Treatment		
	Pre-screening (Visit 1)	Main Study Screening (Visit 2)	1	2	3	4	To be repeated beyond 8 cycles					Safety Follow-up	Survival Follow-Up	
Treatment Cycle/Title:							5	6	7	8				
Scheduling Window (Days):		-28 to -1		± 3	± 3	± 3	± 3	± 3	± 3	± 3	At time of Discon	30 days post discon	Every 12 weeks	
Administrative Procedures														
Pre-screening Consent	X													
Informed Consent		X												
Inclusion/Exclusion Criteria		X												
Demographics and Medical History	X													
Prior and Concomitant Medication Review	X													
Trial Treatment Administration			X	X	X	X	X	X	X	X				
Post-study anticancer therapy status												X	X	
Survival Status						X					X	X	X	X
Clinical Procedures/Assessments														
Review Adverse Events	X	X	X	X	X	X	X	X	X	X	X	X	X	X
Full Physical Examination		X												
Directed Physical Examination	X		X	X	X	X	X	X	X	X				
Vital Signs and Weight	X	X	X	X	X	X	X	X	X	X				
ECOG Performance Status	X	X	X	X	X	X	X	X	X	X				
Laboratory Procedures/Assessments: analysis performed by LOCAL laboratory														
Pregnancy Test – Urine or Serum β-HCG 	X	X	X	X	X	X	X	X	X	X				
PT/INR and aPTT		X				X					X			
CBC with Differential		X	X	X	X	X	X	X	X	X				

Trial Period:	Screening Phase		Treatment Cycles a							End of Treatment	Post-Treatment		
	Pre-screening (Visit 1)	Main Study Screening (Visit 2)	1	2	3	4	To be repeated beyond 8 cycles				Discon	Safety Follow-up	Survival Follow-Up
Treatment Cycle/Title:							5	6	7	8			
Scheduling Window (Days):		-28 to -1		± 3	± 3	± 3	± 3	± 3	± 3	± 3	At time of Discon	30 days post discon	Every 12 weeks
Comprehensive Serum Chemistry Panel		X	X	X	X	X	X	X	X	X			
Urinalysis		X				X				X			
T3, FT4 and TSH		X				X				X			
Efficacy Measurements													
Tumor Imaging			X		X		X		X		X		
Tumor Biopsies/Archival Tissue Collection/Correlative Studies Blood													
Archival or Newly Obtained Tissue Collection			X			X							
Exploratory Biomarker Blood Collection			X				X				X	X	
Anti-Drug Antibodies and Serum Banking			X	X	X						X		

a only in women of child bearing potential

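### The text calls for checks before every weekly sEphB4-HSA dose, but the flow chart shows one set of checks per 3-week cycle, so the Day 8 and Day 15 doses have no charted blood pressure, blood count or liver tests

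*Combined protocol and SAP*

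**What the plan says.** Table 2 in Section 5.2 lists two drugs as trial treatment. Pembrolizumab is given on "Day 1 of each 3 week cycle" and sEphB4-HSA on "Day 1, 8,15 of each 3 week cycle". Section 5.2.2 confirms the weekly schedule: "sEphB4-HSA will be administered as a 60 minute +/- 10 min infusion every week".

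Three text rules attach to every dose. Section 7.1.2.4 asks for "vital signs at screening, prior to the administration of each dose of trial treatment", and it counts blood pressure among the vital signs. Section 7.1.2.5 says the same of ECOG status. Section 7.1.3 says of laboratory tests: "Results must be reviewed by the investigator or qualified designee and found to be acceptable prior to each dose of trial treatment". It also allows pre-dose tests to be done up to 72 hours ahead once Cycle 1 is past.

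The flow chart in Section 6.1 has one column for each of Cycles 1 to 8, to be repeated afterwards. Vital signs, ECOG status, blood count, the "Comprehensive Serum Chemistry Panel" and adverse-event review each carry one mark per cycle. Section 5.2.2 links the chart to a single day: "Trial treatment should be administered on Day 1 of each cycle after all procedures/assessments have been completed as detailed on the Trial Flow Chart".

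The sEphB4-HSA table in Section 5.2.1.3 holds or modifies dosing on AST/ALT, blood pressure, platelets and neutrophils.

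**The concern.** The text and the chart give a site two different instructions for the Day 8 and Day 15 infusions. Coordinators commonly work from the chart. Followed as printed, it would let those doses be given without the measurements that the per-dose text and the dose-modification table presuppose. Section 5.4.2 names hypertension as an expected effect of this drug, and blood pressure is one of the measurements left uncharted.

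Two things are at stake. The first is patient safety before most doses of the weekly agent. The second is uniform detection: a site that follows the text looks three times per cycle and one that follows the chart looks once, so asymptomatic laboratory or blood-pressure changes would be found at different rates for reasons unrelated to the drug.

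**Working it through.** The plan states no figure on this point, so there is none to reproduce. The check is a count, a comparison of times, and a reading of the passages side by side.

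**Inputs.** sEphB4-HSA infusions per cycle: 3 (Table 2). Pembrolizumab infusions per cycle: 1 (Table 2). Chart columns per cycle: 1 (Section 6.1). Laboratory window: 72 h (Section 7.1.3). Allowed shift of Day 1: 3 days either way (Section 5.2.2).

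**1. Doses with no charted check.** Share = (infusions − columns) / infusions.
- Per cycle: (3 − 1)/3 = 2/3, or 66.7%.
- Over 8 charted cycles: 3 × 8 = 24 infusions; 24 − 8 = 16 uncharted. Eight cycles are 24 weeks, close to the 6-month average treatment length in Section 1.0.
- Over 35 cycles, taking the 35 administrations in Section 5.6 as a long-treatment case: 105 infusions; 105 − 35 = 70 uncharted.
- Counting both drugs, 2 of 4 infusions per cycle (50%). The two-thirds figure therefore applies to sEphB4-HSA infusions and to dosing days, not to all infusions.

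**2. Age of Day 1 results at the later doses.** Age = (dosing day − 1) × 24 h.
- Day 8: 7 × 24 = 168 h. Day 15: 14 × 24 = 336 h.
- If Day 1 falls 3 days late and the later doses stay on schedule: (7 − 3) × 24 = 96 h and (14 − 3) × 24 = 264 h.
- All four exceed 72 h. The window is worded for the period after Cycle 1, so the comparison applies strictly to 2 × 7 = 14 of the 16 doses; for the two in Cycle 1 the text gives no window.

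**3. What each measurement feeds.**

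| Measurement | Text | Chart | sEphB4-HSA rule that uses it |
|---|---|---|---|
| Blood pressure | every dose (7.1.2.4) | once per cycle | Grade 2, 3 and 4 hypertension; first versus second Grade 3 |
| AST/ALT | acceptable results before every dose (7.1.3) | once per cycle | Grade 2; Grade 3-4 |
| Platelets, neutrophils | acceptable results before every dose (7.1.3) | once per cycle | Grade 3-4 thrombocytopenia; Grade 4 neutropenia |
| ECOG status | every dose (7.1.2.5) | once per cycle | none |

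**4. Does one mark mean Day 1 or every dosing day?** Three features point to Day 1. The ±3-day window over the columns matches only the window that Section 5.2.2 gives for Day 1. Section 5.2.2 ties completion of the charted procedures to Day 1. The same columns carry imaging and biomarker blood, which are not per-dose procedures, and Section 4.2.3.3 places the on-treatment biomarker blood on day 1. No visible note extends any mark to Day 8 or Day 15.

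**The case against.** The best defence is that the two can be read together. Section 7.1 describes the chart as a summary and leaves the detail to the text, and the text already contains the stricter per-dose rule. The columns are headed by cycle, and the single mark for treatment administration must already stand for three sEphB4-HSA days, so the other marks might do the same. The heading over the treatment cycles also carries a footnote letter whose printed note concerns women of childbearing potential, so a note may have been mislabelled or lost when the PDF was read. This much stands: the checks are missing from the chart, not from the text, and the original chart should be consulted. It does not remove the conflict, because nothing visible tells a site to read the marks that way. Section 7.1.2.4 itself refers back to the chart, and Section 7.1.3 neither names the pre-dose tests nor expressly orders draws on Days 8 and 15.

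A reader might infer three stronger things that the documents do not support.
- *That the toxicity monitoring boundary under-counts.* Section 8.2 defines TOX by treatment discontinuation before the third course, or by immune-related toxicity in the first two courses that does not resolve within 42 days. Discontinuation is known whatever the laboratory schedule, and a brief change that resolves is not a TOX.
- *That events between Day 1 visits go unrecorded.* Section 7.2 requires all adverse events to be reported, Section 7.2.4 requires each grade change to be recorded, and Section 7.1.2.1 provides for additional review when clinically indicated. What could be missed is an asymptomatic change that nobody measured.
- *That the AST/ALT criterion, "if the return to grade 0/1 takes longer than 7 days", cannot be applied.* It starts only after a Grade 2 result has been found and dosing held. The same table cell asks for weekly rechecks after a Grade 3 rise, and Section 5.4.1 suggests weekly tests after Grade 2 hepatic events related to pembrolizumab. It is a follow-up rule that the chart does not schedule, and no more than that.

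**Conclusion.** The inconsistency is real and bears on patient safety. As printed, 2 of every 3 sEphB4-HSA doses have no charted pre-dose check, and Day 1 laboratory results carried forward to those doses would fall outside the plan's own window even with the most favourable allowed shift of Day 1. These are counts of uncharted doses, not of checks shown to have been missed; a site that follows the text would miss none.

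The conclusion rests on two readings: that trial treatment means both drugs, as Table 2 has it, and that a chart mark refers to Day 1, as Section 5.2.2 and the column window indicate. If the original chart carries a note extending its marks to all dosing days, most of the point falls away. The effect on comparability between sites is an inference from the two instructions, not a measured quantity.

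Sections 7.1.2.4 and 7.1.2.5 also call for vital signs and ECOG status at discontinuation, where the chart appears to have no mark. Cells in this table may have shifted on extraction, so that is a matter to check rather than a finding.

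**What to change.** Reconcile Table 2 (Section 5.2), the sEphB4-HSA table in Section 5.2.1.3, and Sections 5.2.2, 6.1, 7.1.2.4, 7.1.2.5 and 7.1.3. The sponsor should decide which passage governs. The flow chart should then state, by Day 1/8/15 columns or by a footnote, which of vital signs, ECOG status, blood count, chemistry and adverse-event review apply before the Day 8 and Day 15 doses, so that chart, text and modification table give one instruction. Section 7.1.3 should name the tests that count as pre-dose and say whether the 72-hour window covers those days. In the same pass, check the discontinuation column of the original chart against Sections 7.1.2.4, 7.1.2.5 and 7.1.4.1, and check the chart's footnote letters.

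The cost is an amendment to the chart and short wording changes. Patients already attend for infusion on Days 8 and 15. If the per-dose text governs, the added cost is local laboratory draws that the text already implies; if the chart governs, the per-dose wording has to change instead. Sample size and analysis are unaffected.
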